The purpose of this novel patient-facing disease management intervention, **My Diabetes GOAL**, is to develop and test a system embedded within the electronic medical record to engage patients in personalized goal setting and chronic disease management by: 1) establishing personalized goals of care based on comorbidities and preferences, 2) tracking diabetes measures against personalized goals, and 3) selecting the route and intensity of care management to help patients achieve their goals (e.g., telephonic care management, in-person care management, and self-care resources). This application can be used to individualize care, increase engagement with patient portals, and improve patient self-efficacy, as they take a more active role in their care.

3. Description of Protocol Methodology:

We will conduct a 6-month randomized controlled trial comparing My Diabetes GOAL vs. usual care within University of Chicago clinics (endocrinology, primary care group, and geriatrics). After agreeing to participate, patients will be randomly assigned to each arm, for a total of 50 patients per arm. Patients that are enrolled in the intervention arm will receive an email message via MyChart to complete the initial questionnaire. If there is an initial non-response, we will try three additional times over a one month period. Completion of the questionnaire will be required prior to initiating risk factor tracking and opening the portal to requests for care management support. Patients enrolled in the usual care will receive the My Diabetes GOAL survey with a 6 months delayed start.

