Prior to receiving the survey, they will be able to continue to receive routine diabetes care and education provided by diabetes educators and clinical staff. Upon completion the study, all patients will receive a post-survey via MyChart. Electronic Health records will be a critical source of data on key processes of care that are affected by My Diabetes GOAL including goal setting measures (documenting personalized goals of diabetes care, proportion following ADA recommendations, proportion choosing alternative goals) as well as referrals to care management and frequency of phone contacts. The EHR will also be the primary source of data for risk factor levels (glycosylated hemoglobin, blood pressure, cholesterol levels), medications, and health care utilization (outpatient visits, care management services, ER visits, and hospitalizations). These data are continually collected as a part of routine care.

4. Duration:

The initial MyChart survey should not take more than 10 minutes to complete. The post-survey should not take more than 5 minutes to complete. Enrollment in services or receipt of telephonic care management is up to the patient, and dependent on their responses to the survey questions. After 6 months, we will terminate telephonic care management follow-up phone calls.

5. Exact Location:

The surveys will be conducted online.

6. Special precautions: n/a

7. Experimental controls:

50 control patients will receive a delayed intervention so we can compare usual care versus the intervention arm, but still distribute the survey and potential telephonic care management to the control arm at a later date. Patients will be the units of randomization. We will enroll patients over 65 years of age with active MyChart accounts, diagnosis of type 2 diabetes, and outpatient clinic visit in the prior year. Because of the general purpose of the intervention, we will not exclude patients with comorbid illnesses or functional impairments. We plan to enroll 100 patients. We will determine trial arm assignment through a random number generator.

8. Outcome measures:

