The primary endpoint is documentation of a personalized goal for diabetes care (e.g., A1C target) (yes or no) in 6 months. Secondary endpoints include patient engagement with MyChart, patient selection of personalized goals, patients' ability to reach their personal treatment goals. We will also collect data on hypoglycemia, psychosocial measures, and health care utilization. It is also possible that changes in patient reported outcomes and utilization will occur earlier than expected through mechanisms that are separate from changes in drug prescribing and risk factor control.

The **documentation measures** (utilization of MyChart, documenting personalized goals of diabetes care, proportion following ADA recommendations, proportion choosing a goal different from the ADA recommendations) will be assessed by comparing results from the EHR at baseline (6 month lookback) and at 6 months of the trial. For **short-term clinical outcomes**, we will evaluate changes

in the proportion of patients with out-of-range A1Cs (A1C>9.0%, A1C<6.5% taking insulin/sulfonylureas) and blood pressures (BP>150/90, BP<120/65). We will also assess changes in the proportion of patients taking statins and specific glucose lowering agents. These analyses will be done for the overall population along with comparisons of drug use by the ADA risk strata. To evaluate **health care utilization**, we will again utilize the EHR to determine the frequency of referrals to telephone care management, the source of referrals (population management, physician), the patient predictors of referrals, and to characterize frequency and content of telephonic management.

9. Statistical analysis:

For the primary endpoint analysis, we will use the Fisher's exact test, and the logistic regression model to compare the two groups. We will also use both the generalized linear mixed model (GLMM) and the generalized estimating equation (GEE) to model % documentation over time (at baseline and 6 months) and test the effects of treatment, time, and interaction between treatment and time. We will first fit unadjusted model and then adjust for potential risk factors such as age, gender, race, and its baseline outcome. Within-subject correlation will be taken into account.

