For the analyses of secondary endpoints, we will conduct between-cohort analyses for those outcomes which can be obtained for both groups, mainly through EHR, and conduct within-cohort analyses for those outcomes which can be collected only in the intervention group.

For between-cohort analyses, for the repeated-measured continuous outcomes such as A1c and BP, we will use a linear mixed model (LMM) to model the outcome over time and test the effects of treatment, time, and treatment-by-time interaction. For the repeated-measured binary outcome such as utilization of MyChart and following ADA recommendations, the same statistical methods as for the primary endpoint will be applied. A Wilcoxon's rank-sum test, and the bootstrapping method will be used to compare frequencies of each type of health care utilization (primary care, emergency room, and hospital visits) for prior 6 months, at baseline and 6 months, and their changed frequencies at 6 months from baseline, respectively. A GEE will also be used to model the frequencies of health care utilization over time.

For within-cohort analyses, i.e., within the intervention group, for the continuous outcome (which will be measured once during the study) such as patient engagement with MyChart, a multiple linear regression will be performed to test the time trend, i.e., conduct self-comparison (post versus before). For the repeated measured binary outcome such as patients' awareness of their A1c goal, both GLMM and GEE will be used to test the time trend. For the binary outcome (which will be measured once during the study) such as achieving their A1c goal at 6 months, the logistic regression model will be used to test the time trend.

We will repeat the analysis plan above, if necessary, at 12 months for the available outcomes from EHR for sustainability check between the groups and/or within cohort.

Power and sample size justification: The primary outcome is documenting personalized goals of diabetes care in 6 months. We expect that at baseline, in both groups, there would have <5% patients whose charts have been documented their personalized goals. We presume that the intervention group will have more than 50%. Using the Fisher's exact test, a total sample size of 44 subjects (22 per group) is needed to obtain at least 90% power to detect the difference between the two groups at a two-sided significance of 5%. With a total sample size of 100, the power will be >0.99.

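### The 6-month goal-attainment endpoint mixes patients who reach their A1C goal with patients who already met it when they chose it

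*Combined protocol and SAP*

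**What the plan says.** **Entry.** Section 7 (Experimental controls) enrols "patients over 65 years of age with active MyChart accounts, diagnosis of type 2 diabetes, and outpatient clinic visit in the prior year". It adds that "we will not exclude patients with comorbid illnesses or functional impairments". That sentence shows a broad population but does not concern A1C. No A1C level, and no requirement to be above a goal, appears among the criteria.

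**Timing of the goal.** Section 3 has patients assigned after they agree to take part, and then: "Patients that are enrolled in the intervention arm will receive an email message via MyChart to complete the initial questionnaire". Up to three further attempts over a month are allowed. Section 9 expects at baseline that "in both groups, there would have <5% patients whose charts have been documented their personalized goals". So for nearly every intervention patient the goal is set after entry.

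**Endpoint and analysis.** Section 8 names "patient selection of personalized goals, patients' ability to reach their personal treatment goals" among the secondary endpoints but gives no baseline condition. Section 9, under the within-cohort analyses, gives "achieving their A1c goal at 6 months" as an example of a binary outcome measured once during the study. It is analysed by logistic regression in the intervention group. Adjustment for the baseline value of the outcome is written for the primary endpoint and carried over to repeated binary outcomes compared between arms. It is not written for this outcome.

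**Possible goals.** The guideline targets cited in Section 1 are A1C below 7.5%, 8.0% or 8.5%, depending on health stratum. Section 8 allows patients to choose a goal that differs from the ADA recommendation.

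**The concern.** The cited A1C targets are upper limits, so a patient can satisfy one on the day it is chosen. Someone with an A1C of 7.2% who selects a goal below 8.0% and does not change counts as a success at 6 months. So does someone who came down from 9% to 7.8%. The endpoint is worded as an ability to reach goals, but only the second patient reached anything.

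The problem lies in who is in the denominator, and no choice of regression model removes it. The reported percentage would move with the A1C mix of those enrolled and with the leniency of their goals, even if the programme helped nobody above goal. It could also rank two programmes the wrong way round, as the working shows.

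**Working it through.** **The plan's own figure.** The plan states no figure for goal attainment. Its only sample-size figure is for the primary endpoint: 5% versus 50%, Fisher's exact test, two-sided 5%, 22 per group for at least 90% power, and power above 0.99 with 100 patients. Exact enumeration gives power 0.927 at 22 per group and 0.9998 at 50 per group (21 per group already gives 0.911). The figure reproduces, and this point does not touch it.

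**Step 1: share at goal when the goal is chosen (assumed distribution).** Take A1C as normal, so that share = Φ((goal − mean)/SD). The means of 7.2 to 7.8% and SDs of 1.0 to 1.5 are assumptions; the goals are those cited in Section 1.

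| Goal | Lowest share | Highest share |
|---|---|---|
| <7.5% | Φ((7.5−7.8)/1.0) = 38% | Φ((7.5−7.2)/1.0) = 62% |
| <8.0% | Φ((8.0−7.8)/1.5) = 55% | Φ((8.0−7.2)/1.0) = 79% |
| <8.5% | Φ((8.5−7.8)/1.5) = 68% | Φ((8.5−7.2)/1.0) = 90% |

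For a central case with mean 7.5, SD 1.3 and goal <8.0%: Φ(0.5/1.3) = Φ(0.385) = 65%.

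**Step 2: patients left above goal in the central case.**
- If all 50 intervention patients set a goal: 50 × 0.65 = 32.5, so about 33 are at goal and about 17 above.
- Section 9 presumes only that more than half will have a documented goal. With 25 patients: 25 × 0.35 = 8.75, about 9.

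**Step 3: who the 6-month achievers are.** Let b be the share at goal when choosing, s the share of those who stay there, and c the share of the others who reach goal. The share of achievers who were already there is b·s / (b·s + (1−b)·c). It exceeds one half when b > c/(s+c). With s = 80 to 90% and c = 10 to 40% (assumptions), that threshold runs from 0.1/(0.9+0.1) = 10% to 0.4/(0.8+0.4) = 33%.

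| b | Share of achievers already at goal |
|---|---|
| 20% | 33 to 69% |
| 38% | 55 to 85% |
| 50% | 67 to 90% |
| 65% | 79 to 94% |

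**Step 4: the pooled rate can mislead.** Assume s = 85%.
- Programme A, with b = 70% and c = 10%: 0.70 × 0.85 + 0.30 × 0.10 = 62.5%.
- Programme B, with b = 30% and c = 40%: 0.30 × 0.85 + 0.70 × 0.40 = 53.5%.

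B moves four times the proportion of above-goal patients, yet it shows the lower attainment rate.

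**Step 5: precision after splitting.** At an assumed 30% reaching goal, the 95% half-width is about 1.96 × √(0.3 × 0.7/n). This gives 22 points for n = 17 and 30 points for n = 9. The approximation is rough at these sizes.

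**The case against.** A reader might infer that the endpoint mostly counts patients with nothing to reach. The documents do not support either half of that.

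- **Mostly.** This needs a baseline A1C distribution and the mix of chosen goals, and neither is given. If 20% start at goal and 30 to 40% of the others reach it, those already there are a minority of achievers (33 to 43%).
- **Nothing to reach.** Staying at goal is a legitimate outcome. The endpoint, "patients' ability to reach their personal treatment goals", covers treatment goals in general, with A1C as the worked example. Section 1 names overtreatment as a concern, and Section 8 counts A1C below 6.5% on insulin or sulfonylureas as out of range. Being under an upper limit is therefore not automatically success.

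Nor can the pooled denominator be blamed for the lack of a causal reading. Usual-care patients get the survey 6 months later and attainment is analysed within one arm, so no effect of the intervention can be read from it whichever denominator is used. Splitting does not cure this. It adds a hazard of its own, because patients selected on a high A1C will tend to fall by regression to the mean. Effects on glycaemia are addressed elsewhere, by the between-arm mixed model for A1C.

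The plan's mention of testing a time trend might suggest that baseline status enters the analysis. It does not, because the outcome is described as measured once.

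All of this stands as a limit on the claim. It leaves untouched that the plan does not separate reaching from staying.

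**Conclusion.** The point holds in a limited form. As written, the endpoint combines two different outcomes under a label that fits only one of them. An unknown and possibly large share of intervention patients may already be at goal when they choose it. The sizes above are conditional on an assumed normal A1C distribution, on assumed rates of staying at and reaching goal, and on how many patients set a goal. None of them is an estimate for this trial. The absence of an A1C entry threshold is not itself a fault, since a broad population suits the purpose of the intervention. The consequence is confined to one secondary, within-arm endpoint.

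**What to change.** Leave eligibility as it is and define the endpoint more closely in Sections 8 and 9:

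1. Take as the denominator the intervention patients with a chosen A1C goal, and state how many that is.
2. Classify each as at goal or not at goal from the last EHR A1C before goal selection. State how many have no usable value.
3. Report reaching goal at 6 months among those not at goal, and remaining at goal among those already there. Give the numerator, denominator and confidence interval for each.
4. Present both as descriptive, noting the missing control comparison and regression to the mean. Rest any claim about glycaemia on the planned between-arm A1C mixed model.

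**Cost.** No new visits or entry criteria are needed, because the EHR is already the source for A1C and the goal is documented as part of the primary endpoint. The work is a definition plus one data-extraction rule. The drawbacks are real. The denominators may be small and the intervals wide. A1C comes from routine care with no measurement scheduled at goal selection, so some baseline values may be old or missing.

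### The A1C and BP mixed model lets the baseline means differ by arm, so its treatment-by-time test is valid but less precise than a common-baseline model or ANCOVA

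*Combined protocol and SAP*

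**What the plan says.** Section 9 (between-cohort analyses) states that "for the repeated-measured continuous outcomes such as A1c and BP, we will use a linear mixed model (LMM) to model the outcome over time". The same sentence says that this model is there to "test the effects of treatment, time, and treatment-by-time interaction". It gives no model equation, covariance structure or coding of time. It does not constrain the baseline means, does not name baseline as a covariate for A1C or BP, and does not say which of the three tests is the treatment effect.

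Baseline adjustment does appear in section 9, but in the primary-endpoint paragraph: the analysts will "adjust for potential risk factors such as age, gender, race, and its baseline outcome". The plan carries those methods over to one other class of outcome only: "repeated-measured binary outcome such as utilization of MyChart and following ADA recommendations, the same statistical methods as for the primary endpoint will be applied". A1C and BP as continuous outcomes are not in that class.

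The baseline and 6-month time points are stated for the primary endpoint (section 9) and for the documentation measures, which "will be assessed by comparing results from the EHR at baseline (6 month lookback) and at 6 months of the trial" (section 8). No schedule is given for A1C and BP. Section 3 says of the record data: "These data are continually collected as a part of routine care".

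**The concern.** A treatment main effect next to a treatment-by-time interaction gives each arm its own baseline mean. In an individually randomised trial (section 7) the arms have the same expected baseline mean, so the extra parameter estimates a quantity known to be zero. A chance baseline imbalance is then subtracted in full from the 6-month difference, when only the part predicted by the baseline-to-6-month correlation should be.

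What is at stake is precision, not validity. With 50 patients per arm and no power calculation for A1C or BP, wider intervals than necessary make these comparisons less informative. The plan could recover that precision from data it already intends to extract.

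**Working it through.** **Inputs from the documents.** 50 patients per arm (section 3); patients individually randomised (section 7); two-sided 5% level (section 9, power paragraph).

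**Assumptions.** Baseline and 6-month values for A1C and BP; A1C SD of 1.2 points at both times; correlation ρ between the two times of 0.3 to 0.9; where missing data are considered, 20% missing independently.

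**1. The plan's own figure.** The only power calculation concerns the binary primary endpoint. Exact two-sided Fisher power for 5% versus 50% is 0.927 at 22 per group and 0.9998 at 50 per group, so the stated figures reproduce. There is no figure for A1C or BP to reproduce.

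**2. What the interaction estimates.** With two times, complete data and free baseline means, the four cell means are unrestricted. The interaction is then (6 months − baseline, intervention) − (6 months − baseline, control), the difference in mean change. Mixed-model fits to simulated trials gave the same value to numerical precision.

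**3. Variances, with n per arm.**
- Planned interaction: (2/n) × 2·SD²·(1 − ρ)
- Common baseline or ANCOVA: (2/n) × SD²·(1 − ρ²)
- Ratio, common baseline to planned: (1 + ρ)/2

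Example at ρ = 0.5: √(0.04 × 2 × 1.44 × 0.5) = 0.240, against √(0.04 × 1.44 × 0.75) = 0.208.

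| ρ | SE planned | SE common baseline | Variance ratio | Planned SE larger by | Detectable difference, 80% power | Power for 0.5 points |
|---|---|---|---|---|---|---|
| 0.3 | 0.284 | 0.229 | 0.65 | 24% | 0.80 vs 0.65 | 0.41 vs 0.58 |
| 0.5 | 0.240 | 0.208 | 0.75 | 15% | 0.68 vs 0.59 | 0.54 vs 0.66 |
| 0.7 | 0.186 | 0.171 | 0.85 | 8% | 0.53 vs 0.49 | 0.76 vs 0.82 |
| 0.9 | 0.107 | 0.105 | 0.95 | 3% | 0.30 vs 0.30 | both above 0.99 |

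The last two columns show planned first and common baseline second, from the noncentral t with 98 and 97 degrees of freedom.

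**4. Cost of estimating the baseline slope.** The factor is 1 + 1/(2n − 4) = 1 + 1/96, about 1% of variance. The ratios become 0.66, 0.76, 0.86 and 0.96.

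**5. Missing or extra values** (generalised least squares, known covariance).
- 20% missing at each time: ratios 0.62, 0.71, 0.81, 0.93; planned SE 27%, 19%, 11%, 4% larger.
- 20% missing at 6 months only: ratios 0.70, 0.79, 0.88, 0.96.
- A complete extra 3-month value, with exchangeable correlation and categorical time: ratios unchanged from the table.

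With missing values the interaction no longer equals the change-score difference exactly, but the baseline means are still free and the loss remains.

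**6. Unequal SDs.** With k = 6-month SD / baseline SD, the ratio is k²(1 − ρ²)/(1 + k² − 2ρk). For k = 1.2 it is 0.76, 0.87, 0.97, 0.98; for k = 0.8 it is 0.50, 0.57, 0.63, 0.61. The per-patient variance difference is (SD₀ − ρ·SD₁)², where SD₀ and SD₁ are the baseline and 6-month SDs. It is never negative, so with complete data and known covariance the planned contrast can at best tie.

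**7. Validity.** In 4,000 simulated trials at each of ρ = 0.5 and 0.7, type I error of the planned test was 0.053 and 0.048, against 0.049 and 0.051 for ANCOVA. The planned-to-ANCOVA variance ratio was 1.31 and 1.16, against 1.33 and 1.18 in theory. In a second simulation (600 trials per scenario, true effect −0.5, complete data or 20% missing at each time), mean estimates from the free-baseline and common-baseline models lay between −0.49 and −0.52.

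**8. Would borrowing the primary-endpoint adjustment help?** No. If baseline stays as a response row and is also entered as a patient-level covariate without a covariate-by-time term, it cancels out of the within-patient change. The complete-data interaction estimate does not move.

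**The case against.** The strongest reply is that nothing here is wrong. The model is a standard repeated-measures analysis, its interaction test is valid, and the interaction is the obvious treatment contrast. Mean A1C and BP are also peripheral. Section 8 frames the short-term clinical outcomes as proportions out of range in either direction, and the background is concerned with both over- and undertreatment, so a mean shift is not the trial's stated hypothesis. The size of the loss is wholly assumed: if the 6-month SD is 1.2 times the baseline SD, the planned SE is only about 1% to 2% too large at ρ of 0.7 to 0.9. Finally, the model form is inferred from a short list of tested effects.

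Much of this stands, and it limits the grade. The 0.5-point power comparison is an illustration, not a planned effect. The loss could be trivial, and the reading of the model is the natural one but not the only possible one. The objection does not remove the point. Section 9 does plan a between-arm comparison of continuous A1C and BP. The efficient model targets the same 6-month difference from the same data. The unequal-SD argument also runs the other way: at k = 0.8 the loss is larger than in the equal-SD table.

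**Conclusion.** The concern holds as a minor point of efficiency. As written, the A1C and BP model leaves the baseline means free, and its interaction test is unbiased but less precise than it could be. With equal SDs the planned standard error is 3% to 24% larger than necessary with complete data, and 4% to 27% larger with 20% of values missing at each time, over correlations from 0.9 down to 0.3. At a correlation of 0.9 the practical gain is small.

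The algebra is certain. The size rests on an assumed correlation, SD ratio, schedule and missing-data pattern, none of which the documents give. Selective measurement in routine care could affect every model considered here and is a separate matter.

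**What to change.** For A1C and BP, fit the mixed model with categorical time and treatment-by-time but no treatment main effect, so that the baseline means are equal across arms, with an unstructured within-patient covariance. Name the 6-month between-arm difference, with its 95% CI, as the treatment effect.

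ANCOVA of the 6-month value on arm and pre-randomisation baseline, with baseline not kept as a response row, is an acceptable alternative when data are complete. It drops patients who lack either value. With 20% missing at each time, 50 × 0.8 × 0.8 = 32 per arm remain, and the SEs at ρ = 0.3, 0.5, 0.7, 0.9 are:

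| Analysis | 0.3 | 0.5 | 0.7 | 0.9 |
|---|---|---|---|---|
| Planned model | 0.327 | 0.283 | 0.224 | 0.133 |
| Complete-case ANCOVA | 0.286 | 0.260 | 0.214 | 0.131 |
| Common-baseline model | 0.258 | 0.238 | 0.202 | 0.128 |

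Allowing for slope estimation (factor 1 + 1/60) raises the ANCOVA row to 0.289, 0.262, 0.216, 0.132. The common-baseline model is therefore the better choice where values may be missing.

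The cost is analysis wording plus one definition: a pre-randomisation baseline window for A1C and BP. The 6-month lookback in section 8 is stated for the documentation measures, and eligibility in section 7 asks only for "diagnosis of type 2 diabetes, and outpatient clinic visit in the prior year", so some patients may have no value in whatever window is chosen. No new data, visits or patients are needed.

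### MyChart engagement is undefined and tested before-after in the intervention arm only; if it means portal activity, the plan's own rule calls for a between-arm comparison

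*Combined protocol and SAP*

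**What the plan says.** Section 8 (Outcome measures) states: "Secondary endpoints include patient engagement with MyChart". It is the first secondary endpoint listed, and Section 2 gives greater engagement with patient portals as one use of the application. No section states its unit, time window or source.

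Section 9 (Statistical analysis) sorts secondary endpoints by a rule. It plans "between-cohort analyses for those outcomes which can be obtained for both groups, mainly through EHR", and will "conduct within-cohort analyses for those outcomes which can be collected only in the intervention group". Engagement appears in the second set: "for the continuous outcome (which will be measured once during the study) such as patient engagement with MyChart", for which "a multiple linear regression will be performed to test the time trend, i.e., conduct self-comparison (post versus before").

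A closely related measure is treated differently. Section 8 lists utilization of MyChart among the documentation measures, which "will be assessed by comparing results from the EHR at baseline (6 month lookback) and at 6 months of the trial". Section 9 puts it in the between-cohort set: "For the repeated-measured binary outcome such as utilization of MyChart and following ADA recommendations" are to be analysed with the primary-endpoint methods. The plan does not say how engagement differs from utilization.

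**The concern.** Two things look wrong. First, one measurement and a post-versus-before test do not obviously fit together, and without a metric the analyst has to choose the outcome and the model. Second, if engagement is portal activity, it has been put in the wrong set under the plan's own rule.

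At stake is the interpretation of one secondary endpoint that reflects a stated aim of the application. If portal use changes over six months for reasons that affect all patients, the intervention-arm test reports that change as a result. The trial has a randomised control arm that could remove it.

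**Working it through.** **Plan's own figure.** The documents give no figure for engagement. The only calculation in Section 9 concerns the primary endpoint (5% versus 50%, Fisher's exact test, two-sided 5%). Exact enumeration gives power of 0.927 at 22 per group and 0.9998 at 50 per group, which agrees with the stated values of at least 90% and above 0.99. It has no bearing on this point.

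**What engagement could mean.**

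- *Portal activity, including one on-study value against the look-back.* Section 7 requires an active MyChart account of every participant. Section 8 reads MyChart utilization from the EHR at look-back and at month 6. Portal activity is therefore available in both arms, and the Section 9 rule calls for a between-cohort analysis. The look-back reading eases the conflict over measuring once, but it relies on the same EHR data and so leads to the same conclusion.
- *Use of the My Diabetes GOAL module.* Under Section 3, tracking and care-management requests open only after the questionnaire, and controls start 6 months later. Intervention-only placement fits the rule, but there is no earlier value to compare with.
- *A survey score.* Controls receive the initial survey only after the delay, so a before-after score up to month 6 would exist in the intervention arm only, and it would be measured twice. Section 3 sends the post-survey to all patients, so a post-survey score could also be compared between arms.

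**Illustration of the single-arm test.** The only document inputs are 50 patients per arm (Section 3) and, borrowed from the primary endpoint, two-sided 5%. Assumed inputs are equal SDs before and after, correlation r of 0.3 to 0.7, a drift common to both arms, and no treatment effect. In SD units the standard error of the mean change is √(2(1−r)/50). Rejection rates come from the noncentral t distribution.

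| r | SE of change | 0.2 drift ÷ SE | Rejection at drift 0.1 / 0.2 / 0.3 SD |
|---|---|---|---|
| 0.3 | √(1.4/50) = 0.167 | 1.20 | 9.0% / 21.6% / 42.0% |
| 0.5 | √(1.0/50) = 0.141 | 1.41 | 10.7% / 28.4% / 54.8% |
| 0.7 | √(0.6/50) = 0.110 | 1.83 | 14.6% / 43.3% / 76.6% |

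In a between-arm comparison the drift cancels. Simulated rejection under the same drifts was 4.8-5.3%.

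The plan also does not say whether the regression models a change score. If it stacked two rows per patient and ignored the pairing, the standard error would be √(2/50) = 0.200. That is too large by a factor 1/√(1−r), or 1.20, 1.41 and 1.83 at the three correlations.

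**What a between-arm test could detect.** For 50 per arm and 80% power the multiplier is 1.960 + 0.842 = 2.802. Values in parentheses use the t distribution.

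| r | Month 6 adjusted for look-back: 2.802·√(2(1−r²)/50) | LMM treatment-by-time, baseline unconstrained: 2.802·√(4(1−r)/50) |
|---|---|---|
| 0.3 | 0.535 (0.540) SD | 0.663 (0.670) SD |
| 0.5 | 0.485 (0.490) SD | 0.560 (0.566) SD |
| 0.7 | 0.400 (0.404) SD | 0.434 (0.438) SD |

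Detectable differences thus run from about 0.40 to 0.67 SD.

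**The case against.** The strongest reply is that the sentence can be read coherently: one value during the study, with the look-back as the comparator. A reader might infer that the sentence contradicts itself on every reading, and the documents do not support that. Two limits remain. Section 9 calls MyChart utilization, which has the same look-back, repeatedly measured, so the wording is still unclear. And this reading depends on EHR portal data that controls have too.

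Second, engagement may mean module use or a survey score, and intervention-only placement could then be right. This stands, and it is why the breach of the plan's rule is conditional.

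Third, portal use already has a randomised comparison through binary utilization, and the plan openly labels the engagement test a self-comparison without claiming causation. This also stands. A reader might infer that portal use goes without any controlled analysis; it does not. The gap is the continuous measure.

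Fourth, nothing in the documents suggests that portal use drifts. That is correct. The drift figures show a general property of before-after tests and are not evidence about this trial.

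Finally, a between-arm difference would partly count log-ins prompted by the study's own messages. Section 3 describes a questionnaire invitation and up to three further tries in the intervention arm, and a post-survey for all. Section 13 describes a survey invitation after consent without restricting it to one arm. The caution is fair, but its size cannot be estimated from the documents.

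**Conclusion.** The concern holds in conditional form. It is certain from the text that engagement has no metric or source, and that it is assigned to an intervention-only post-versus-before test while described as measured once. If it means portal activity, including on the look-back reading, the placement departs from the plan's own rule and gives up the control for common change that randomisation provides.

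The size is modest. One secondary endpoint is affected and should be corrected. The primary endpoint and the between-arm analyses of A1c, blood pressure, binary MyChart utilization and health care utilization are untouched. The 22-43% false-positive range rests wholly on an assumed 0.2 SD drift and correlations of 0.3-0.7, and should not be read as a forecast.

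**What to change.** Define engagement as EHR portal activity per 6 months (for example log-ins or messages), and say how it differs from utilization. Correct the statement that it is measured once. Move it to the between-cohort analyses, using the LMM already planned for repeated continuous outcomes or comparing month-6 use adjusted for look-back use.

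If the sponsor means something else:

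- *Module use:* report month-6 use in the intervention arm, with no before-after test.
- *Survey score:* state when it is measured, account for within-patient correlation in any pre-post test, and compare arms on the post-survey score. Section 3 times that survey only by study completion, so state that controls answer it before their delayed start.

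Label any single-arm before-after result descriptive.

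The cost is SAP wording and an EHR pull of counts rather than yes/no values. The EHR data list in Section 3 does not name portal counts, so availability must be checked. No extra patient contact is needed. With 50 per arm only moderate differences are detectable, about 0.40-0.67 SD under the assumed correlations. The report should also caution that some intervention-arm log-ins will come from the study's own MyChart messages.
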